## 2 Study Purpose

### 2.1 Objectives

#### Primary Objective

To assess whether the IMR can be considered a prognostic predictor for the occurrence of events (as hereinafter further defined) at one year of follow up after primary PCI in STEMI patients.

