### 2.2.2 Secondary Endpoints

- Evaluation of a better cut-off of IMR index based on primary endpoint events
- New CHF during index hospitalization
- Left Ventricular (LV) remodeling @ 1y (improvement of EF%, LVESV, LVEDV, LVEDD, LVESD, 16 segments WMSI and mitral insufficiency, assessed by TTE)
- Need for new revascularization @ 1y (revascularization yes/no)
- Stent thrombosis @ 1y (thrombosis yes/no)
- ST resolution or residual ST elevation post PCI (Electrocardiographic ST-segment elevation in two or more contiguous electrocardiogram (ECG) leads)
- Evaluation of possible events predictors including but not limited to age, sex, infarct area, Killip risk, number of PCI

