### 2.4 Study Design

This is a prospective, multicenter study designed to evaluate IMR ability to predict events occurrence, defined as Cardiovascular death, re-MI, re-hospitalization for HF, resuscitation or ICD appropriate shock, during a 1 year follow-up period.

[figure not shown]
Patients will be enrolled in the study at hospital admission after the pathology assessment has been done. All participants will have the culprit lesion treated following clinical practice and guidelines ; Fractional Flow Reserve (FFR) and IMR will be measured after the primary PCI procedure to evaluate treatment success and myocardial viability. Non-culprit lesions will be functionally evaluated through FFR index and will be treated if FFR will show functional stenosis . FFR and IMR will be measured to evaluate treatment success and myocardial viability. Patients will be followed-up at 1m, 6m and 1y periods.

Device used to assess FFR and IMR is already in use in clinical practice at participating centres. The wire is used following indication for use (IFU), guidelines and clinical practice in the selected centers.

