### **3.2.1 Procedures**

Primary PCI is performed as soon as possible, following the center clinical practice, to treat the culprit lesion. Drug Eluting Stent (DES) of choice in the center and required by the lesion anatomy will be used following the usual clinical practice. FFR and IMR will be measured at the end of the procedure.

Staged procedure to treat the non-culprit lesion will be performed before hospital discharge as per normal clinical practice of the center. FFR and IMR will be measured and lesion will be treated only if FFR will show functional stenosis. Distal lesion that can't be crossed with the guidewire will be treated as per clinical practice. Drug Eluting Stent (DES) of choice in the center and required by the lesion anatomy will be used following the normal clinical practice in each center. FFR and IMR will be measured at the end of the procedure. An ECG will be assessed approximately 90 minutes after primary PCI procedure. A TTE (Echo) will be performed before the patient discharge.

Medical therapy during the procedure and at the hospital discharge will be driven by usual clinical practice, guidelines and standard of care recommendations.

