#### **Secondary Objective Analysis:**

IMR analysis as a possible predictive index will initially be carried out by evaluating whether there are quantiles that better identify classes of patients with higher risk of defined major cardiac event.

Discriminant model (ROC curve) will allow to assess whether there are IMR-threshold values (cut-off) to allow classification of patients at increased or decreased risk of future events.

The analysis of variance (ANOVA) for repeated measures or the analysis of covariance (ANCOVA) to multiple factors will be used to assess whether there are significant changes in continuous parameters during post-intervention.

Kaplan-Meier analysis of event-free survival (EFS) allows the assessment of possible risk factors (gender, age, smoking, cholesterol, etc...) testing the significance by log-rank test.

The significant results and other factors considered clinically relevant will be included, as independent variables in a Cox regression model having the appearance or not of composite event and the time as dependent variables.

Where multiple comparisons will be assessed, corrections for multiple comparisons will be applied and specified as needed.

Values of  $p < 0.05$  are considered statistically significant.

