### 6.2 Study Investigators

This clinical study will be conducted by qualified investigators who have experience with the use of device. Qualified Investigators are familiar with the PCI optimization by the assessment of stenosis functional evaluation through FFR and with IMR index for the myocardial viability assessment.

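### Does the LV remodelling analysis need a named IMR term?

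*Combined protocol and SAP*

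**What the plan says.** Section 2.2.2 lists as one secondary endpoint "Left Ventricular (LV) remodeling @ 1y (improvement of EF%, LVESV, LVEDV, LVEDD, LVESD", followed by wall motion score and mitral insufficiency, all from transthoracic echo. Section 2.1 lists remodelling among items to be evaluated, without mentioning IMR. Echo is scheduled before discharge and at 12 months (Tables 1 and 2).

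One inferential sentence in section 4.2 suits continuous measures of this kind. It offers repeated-measures ANOVA or "the analysis of covariance (ANCOVA) to multiple factors", "used to assess whether there are significant changes in continuous parameters during post-intervention". The factors are not named. Section 4.2 also provides descriptive summaries and 95% confidence intervals for continuous variables.

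The analyses in section 4.2 that name IMR all have events as their outcome: the primary chi-square test, the search for informative quantiles and the ROC cut-off. On multiplicity the section says "Where multiple comparisons will be assessed, corrections for multiple comparisons will be applied and specified as needed".

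IMR's role is described elsewhere. The primary objective is "To assess whether the IMR can be considered a prognostic predictor for the occurrence of events" at one year. Section 2.4 says "IMR will be measured after the primary PCI procedure to evaluate treatment success and myocardial viability", and section 6.2 expects investigators to be familiar "with IMR index for the myocardial viability assessment".

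**The concern.** The study exists to find out what IMR predicts, and left ventricular remodelling is a natural thing for it to predict. Section 1 (Background) cites earlier work linking IMR to recovery of the ventricle, and sections 2.4 and 6.2 say that IMR is measured to judge viability. A reader would expect the remodelling endpoint to be analysed against IMR.

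The sentence in section 4.2 does not do that. The study is a single cohort with two echo examinations, so repeated-measures ANOVA on time alone reduces to a paired before-and-after comparison and carries no information on IMR. The ANCOVA option might include IMR, but its factors are unlisted. An association between IMR and remodelling would then either go unestimated or be estimated with a model chosen after the data were seen.

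The choice of IMR value also looks open. Section 3.2.1 has IMR measured after primary PCI and, for the staged non-culprit procedure, says "FFR and IMR will be measured and lesion will be treated only if FFR will show functional stenosis". A patient may therefore have more than one value.

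**Working it through.** **Endpoint against analysis**

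| Element | Where | Is IMR tied to remodelling? |
|---|---|---|
| Objective: evaluate remodelling | 2.1 | No |
| Endpoint: improvement in echo measures at 1 year | 2.2.2 | No |
| Data: echo pre-discharge and at 12 months | Tables 1 and 2 | Not applicable |
| Method: test of change after the intervention | 4.2 | No |
| Study purpose: IMR against clinical outcomes | 1 | No; the outcomes listed are all events |

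The objective, endpoint, data and method agree with one another. Improvement is change between two times, and the method tests change between two times. The background text is the closest the documents come to linking IMR with the ventricle. It presents that link as already reported and then places the open question in short- and mid-term clinical outcomes. Sections 2.4 and 6.2 explain why IMR is measured during the procedure. They do not set out an echo analysis.

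**The plan's own figure**

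Inputs from section 4.1: event rates 7% and 21%, two-sided alpha 0.05, power 85%, equal groups from the median split. With mean rate 0.14:

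n per group = [1.960·√(2·0.14·0.86) + 1.036·√(0.07·0.93 + 0.21·0.79)]² / 0.14² = 108.7, so 109 per group and 218 in total. Then 218/0.9 = 242.2, which agrees with the 242 stated. No echo quantity enters this calculation.

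**What an added IMR term might show (all echo inputs assumed)**

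Model: 12-month EF = s × (pre-discharge EF) + b × (IMR in SD units) + error. Assumed: b = −2 EF points, pre-discharge SD 10, s = 0.6, SD of change 8 or 10, correlation r between IMR and pre-discharge EF of 0 or −0.4, and 180 or 218 pairs.

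- Residual variance = SD² − [(s−1)²·100 + b² + 2(s−1)·b·r·10]. At SD 8 and r = 0 this is 64 − (16 + 4) = 44. At r = −0.4 it is 64 − (16 + 4 − 6.4) = 50.4.
- SE of b = √[residual variance / ((n−1)(1−r²))]. At n = 180 this gives √(44/179) = 0.496 and √(50.4/(179·0.84)) = 0.579.
- Power (noncentral t, n−3 df) at SD 8: 98% (r = 0) and 93% (r = −0.4) with 180 pairs; 99% and 97% with 218. At SD 10: 85% and 75% with 180; 91% and 82% with 218.
- The time-by-IMR (change-score) coefficient is b + (s−1)·r·10. It equals −2.0 at r = 0 and −2 + 1.6 = −0.4 at r = −0.4. At SD 8 its power falls from 93–97% to 10–11%.
- With b = 0 and r = −0.4, ANCOVA has a true coefficient of 0, while the change score has one of +1.6 and rejects in 78% (180 pairs) to 85% (218 pairs) of studies at SD 8.

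So an IMR term could be informative under these assumptions, but the two obvious ways of adding it need not agree. Reporting both for six measures, plus an ordinal model for mitral insufficiency, makes 6 + 6 + 1 = 13 estimates. A Bonferroni correction of the six ANCOVA terms alone (0.05/6) lowers ANCOVA power to 78–96% at SD 8 and 49–74% at SD 10. Over all 13 (0.05/13) it falls to 70–93% and 39–65%.

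**The case for a change.** The best case for a change is that it is cheap and the sentence is incomplete. IMR and both echoes are already collected, ANCOVA is already named, and a few sentences would fix the model in advance. An ANCOVA with unlisted factors is undefined until someone lists them, and the choice between the two methods is left open. The illustration shows that two defensible IMR analyses could give different conclusions.

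Part of this stands: the factors are unlisted, and the documents never say whether IMR is one of them. The step from there to a required IMR term does not. The link is inferred from the study's subject, and no stated objective asks for it. New revascularisation, stent thrombosis, ST resolution and in-hospital heart failure are likewise listed without IMR, and nothing singles out remodelling. The divergence between ANCOVA and change score belongs to the proposed addition, because the plan commits to neither IMR estimate. Reporting both without saying which governs would bring back the choice after the data are seen. The addition would also have to deal with the fact that 12-month echo exists only for survivors who attend, while the study hypothesises that IMR predicts a composite including cardiovascular death.

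Which IMR value to use is not specific to this endpoint. The chi-square sentence in section 4.2 names no vessel either, and the footnote in section 2.2.1 points to the culprit lesion.

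**Conclusion.** No change to the plan is called for. The observation is accurate: the one inferential sentence that fits the continuous echo measures targets change over time and names no IMR term. But that is what the endpoint asks for, and the analysis as written answers it. The unlisted factors are ordinary missing detail for one secondary endpoint, which an analyst can fill sensibly, and the existing multiplicity statement already covers comparisons added at that stage.

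The primary test is unaffected, and its 218 evaluable and 242 enrolled patients reproduce. The power figures for an IMR term (75–99% uncorrected at slope 0.6 and SD of change 8 or 10) rest wholly on assumed echo inputs and describe a model outside the plan, so they do not measure a fault in it. The conclusion rests on reading the remodelling objective as worded. If the sponsor did intend to relate remodelling to IMR, that would be an additional, exploratory question.

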## 4 Scientific Soundness

### 4.1 Sample Size

Study aim is to assess/explore, in a cohort of STEMI patients at 1 year of follow-up from primary PCI, if categorization of IMR based on the median value can be considered a predictive / prognostic for the occurrence of cardiovascular events such as death, re-MI, re-hospitalization for HF, resuscitation or appropriate ICD shocks.

It is believed, based on the events reported in similar cohort of patients , that the expected events at one year should be of 12-16%.

The present study aims to demonstrate that the incidence of events is significantly different in the two subpopulations of patients with IMR upper and lower of the value of 32, found by Fearon et al.; other authors found the median value as event predictor.

Based on these assumptions, hypothesizing an incidence of events/year by 7% in the group of patients with IMR values below its median and 21% in the group with higher values of IMR, with an alpha error = 0.05, a power of 85% and applying the two tails Chi-square test, it is estimated that 218 patients are needed.

Providing a dropout rate of 10%, the number of patients who must be enrolled will be 242.

It is assumed that the participant centers will be up to 20. Based on number of cases in previous year evaluation, enrollment mean rate is assumed to be approximately 6-10 patients/year/center.

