#### **Primary Objective Analysis:**

The Chi-square test will be used to evaluate the existence of associations between IMR-values (above and below the median) and the outcome.

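### Testing age and cholesterol by log-rank forces unspecified grouping; a median split would keep only about 64% of the information from roughly 30 events

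*Combined protocol and SAP*

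**What the plan says.** Section 2.2.2 lists as a secondary endpoint "Evaluation of possible events predictors including but not limited to age, sex, infarct area, Killip risk, number of PCI". Section 4.2, under Secondary Objective Analysis, gives the method: "Kaplan-Meier analysis of event-free survival (EFS) allows the assessment of possible risk factors (gender, age, smoking, cholesterol, etc...) testing the significance by log-rank test". Two of the four named factors, age and cholesterol, are measured on a continuous scale.

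The next sentence of 4.2 takes the significant factors into a Cox model for the composite event. It also admits further factors judged clinically important. Neither sentence gives cut-points, a number of groups or a grouping rule, and the coding of continuous factors in the Cox model is not stated. Multiplicity corrections are left to be applied and specified where needed.

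Section 4.1 states "that the expected events at one year should be of 12-16" per cent. It gives no power, effect size or event count for the predictor analysis.

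**The concern.** The log-rank test compares survival curves between groups. To apply it to age or cholesterol, someone must first choose where to cut. This has two consequences.

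- **Loss of information.** All patients on one side of a cut are treated as alike. With few events the study can detect only fairly strong predictors even at full efficiency, so a real predictor becomes easier to miss.
- **Dependence on the cut.** Different reasonable cuts give different p-values, and nothing in the plan fixes the cut before the data are seen.

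At stake is the reported univariable result for each continuous factor and, through it, the evidence on which factors are chosen for the Cox model.

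**Working it through.** **1. The plan's own sample size.** Section 4.1 takes one-year event rates of 7% for the low-IMR half and 21% for the high-IMR half. The error rates and the test are set there too: "with an alpha error = 0.05, a power of 85% and applying the two tails Chi-square test". Section 4.2 splits "IMR-values (above and below the median) and the outcome", so the groups are equal and the pooled rate is (7 + 21)/2 = 14%. With the pooled-variance formula,

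n per group = [1.96·√(2·0.14·0.86) + 1.036·√(0.07·0.93 + 0.21·0.79)]² / 0.14² = (0.962 + 0.498)² / 0.0196 = 108.7, rounded up to 109.

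Twice 109 is 218, which matches "it is estimated that 218 patients are needed". The primary calculation reproduces.

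**2. Events available.** 218 × 0.12 = 26.2, 218 × 0.14 = 30.5 and 218 × 0.16 = 34.9. If all 242 enrolled patients contribute, the range is 29.0 to 38.7.

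**3. Information kept by a median split.** For a normal predictor, the squared correlation between the value and an above-median indicator is φ(0)² / (0.5 × 0.5) = 0.159/0.25 = 2/π = 0.637. So 30.5 events do the work of 30.5 × 0.637 = 19.4. To a first approximation this ratio does not depend on the hazard ratio.

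**4. Power.** Let D be the number of events and HR the hazard ratio per SD, two-sided 5% level:

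- measured value: Φ(√D · ln HR − 1.96)
- median split: Φ(√(0.637·D) · ln HR − 1.96)

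Example, D = 30.5 and HR = 1.6 (ln HR = 0.470):

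- measured value: Φ(5.523 × 0.470 − 1.96) = Φ(0.636) = 0.74
- median split: Φ(4.406 × 0.470 − 1.96) = Φ(0.111) = 0.54

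The documents give no HR for any predictor, so a range is shown. The simulation used 218 patients, 14% events at one year and 6,000 cohorts per row, comparing the Cox score test on the measured value with the log-rank test at the median.

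| HR per SD | Formula: measured / split | Loss (points) | Simulated: measured / split | Loss (points) |
|---|---|---|---|---|
| 1.3 | 0.31 / 0.21 | 9 | 0.30 / 0.20 | 10 |
| 1.4 | 0.46 / 0.32 | 14 | 0.46 / 0.31 | 15 |
| 1.5 | 0.61 / 0.43 | 18 | 0.60 / 0.40 | 20 |
| 1.6 | 0.74 / 0.54 | 19 | 0.72 / 0.53 | 20 |
| 1.7 | 0.83 / 0.65 | 19 | 0.82 / 0.60 | 21 |
| 1.8 | 0.90 / 0.74 | 17 | 0.88 / 0.69 | 19 |
| 2.0 | 0.97 / 0.86 | 11 | 0.96 / 0.83 | 13 |

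With no effect, the rejection rates were 0.051 and 0.049. Adding 10% random early censoring (about 29 observed events) gave 0.57 / 0.39 at HR 1.5, 0.71 / 0.50 at 1.6, 0.87 / 0.68 at 1.8 and 0.95 / 0.80 at 2.0. By formula the loss peaks at 19.4 points, where the measured-value test has about 75% power. At 26 events the formula losses run from 8 points (HR 1.3) through 19 (HR 1.67) to 14 (HR 2.0).

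**5. Events needed for 80% power at HR 1.7.** (1.96 + 0.842)² / (ln 1.7)² = 7.85/0.2816 = 27.9 for the measured value, and 27.9/0.637 = 43.8 for the median split. The first lies within the expected 26 to 35 events; the second does not.

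**6. Dependence on the cut** (simulated, HR 1.6, about 29 events). Log-rank power was 0.31 with a cut at the lower quartile, 0.50 at the median and 0.54 at the upper tertile, against 0.70 for the measured value. The median and upper-tertile cuts disagreed on significance in about 25% of cohorts. With no effect, taking the best of five ordinary cuts (median, outer quartiles, tertiles) gave p < 0.05 in about 15% of cohorts.

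**The case against.** The case for leaving the plan alone has five parts.

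- **The median split is not in the plan for these factors.** This stands. The only median in 4.2 concerns IMR. With ordered quartiles and a trend test, simulated power was 0.51 against 0.58 for the measured value at HR 1.5, 0.62 against 0.69 at 1.6, and 0.80 against 0.87 at 1.8; repeat runs put this loss at about 5 to 8 points. A poorly placed cut would lose more than the median does.
- **The comparison favours the fix by assuming log-linearity.** This stands in part. If risk steps up exactly at the median, the split wins: 0.62 against 0.47 for a step of HR 2.5, and 0.75 against 0.60 for HR 3. That advantage needs the cut to fall at the step, and the plan offers no basis for placing it there.
- **A factor missed by the screen is not necessarily lost.** This stands. Section 4.2 also lets factors judged clinically important into the Cox model, and age is already named in 2.2.2. Nothing requires grouped coding in that model. However, the choice rests on unspecified judgement, and the univariable result is still reported.
- **The scope is narrow.** This stands. Gender and smoking are unaffected as usually recorded, as are sex and Killip class in 2.2.2.
- **The search is exploratory and the sequence conventional.** True, and no protocol decision rests on it. That limits the importance of the point but gives no reason to prefer the weaker test.

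**Conclusion.** The point holds for the univariable screen of continuous factors. As written, 4.2 needs age and cholesterol to be grouped at cuts that it does not state, and the resulting p-value depends on those cuts.

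The size is conditional. For a normal, log-linear predictor split at its median, about 64% of the information is kept. At about 30 events that costs roughly 9 to 21 points of power over HR 1.3 to 2.0 per SD. The largest losses, about 18 to 21 points, arise by simulation at HR of about 1.5 to 1.8; the formula gives about 17 to 19 there.

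Three stronger readings are not supported:

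- A reader might take 18 to 21 points as a fixed cost of the plan. It is near the worst case for a median split, and neither the split nor the HR is in the documents.
- A reader might infer that a predictor missed by log-rank is shut out of the Cox model. Section 4.2 allows it in on clinical grounds.
- A reader might infer that the primary analysis is underpowered for this reason. The chi-square test and its 218 patients do not depend on this screen.

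**What to change.** In section 4.2, under Secondary Objective Analysis:

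- Test continuous factors (age, cholesterol and any other measured on a scale) by univariable Cox regression on the measured value. Report the hazard ratio per fixed, stated unit with its 95% confidence interval.
- Enter these factors on the same continuous scale in the multivariable Cox model.
- Keep the log-rank test for categorical factors such as gender and smoking.
- Use Kaplan-Meier curves of grouped continuous factors for display only, without a test, at cut-points stated in advance.

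The cost is wording. Cox regression is already planned, and no new data, patients or software are needed. The downside is small: log-linearity is assumed, a residual plot can check it only weakly with about 30 events, and power is lower than for a split if the true effect is a step at that split.

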### 4.2 Statistical Methods

Data analysis will begin when all patients enrolled in the specified period will have completed 12 months of follow-up.

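### The secondary Cox model screens its terms by p-value, neither requires IMR nor fixes its form, and the ROC cut-off is judged in the data that chose it

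*Combined protocol and SAP*

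**What the plan says.** The primary objective (section 2.1) is "To assess whether the IMR can be considered a prognostic predictor for the occurrence of events" at one year. The primary analysis in section 4.2 is unadjusted: "The Chi-square test will be used to evaluate the existence of associations between IMR-values (above and below the median) and the outcome".

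The Secondary Objective Analysis then describes, in this order:

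- a search over IMR quantiles, "evaluating whether there are quantiles that better identify classes of patients with higher risk of defined major cardiac event";
- a ROC search for a threshold: "Discriminant model (ROC curve) will allow to assess whether there are IMR-threshold values (cut-off";
- ANOVA or ANCOVA, for continuous parameters only;
- Kaplan-Meier screening of "possible risk factors (gender, age, smoking, cholesterol, etc...) testing the significance by log-rank test";
- a Cox model for the composite: "The significant results and other factors considered clinically relevant will be included, as independent variables in a Cox regression model".

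On multiplicity it says only that "corrections for multiple comparisons will be applied and specified as needed".

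The screening list and the predictor list in section 2.2.2 are both open-ended, and neither names IMR. Section 4.1 refers to the median and also to a fixed value of 32 taken from a cited study. No sentence describes validation of a cut-off, a fixed covariate set, or a limit on the number of Cox terms.

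**The concern.** A significant chi-square shows that IMR is associated with events. It does not show whether IMR adds anything to age or Killip class. The Cox model is the only planned analysis in which IMR could be seen beside other predictors of the composite, and three things about it are left open: whether IMR is in it, in what form, and with which covariates.

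The form matters most. The documents mention a median split, a value of 32, a better quantile and a ROC cut-off. The last two would be found by looking at the outcome. A cut-off chosen because it separates events best will look better in those data than in new patients. If it also became the Cox term, the p-value and hazard ratio would inherit that optimism. The multiplicity sentence ties no correction to this choice.

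**Working it through.** **The plan's own figure.** Inputs from section 4.1: 7% and 21%, two-sided alpha 0.05, power 85%, equal groups (implied by the median split). With pooled variance:

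n per group = [1.960 × √(2 × 0.14 × 0.86) + 1.036 × √(0.07 × 0.93 + 0.21 × 0.79)]² / 0.14² = (0.962 + 0.498)² / 0.0196 = 108.7

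The total is 217.5, i.e. 218, and 109 per group gives 85.1% power. Dropout: 218 / 0.9 = 242.2, against 242 stated. The primary calculation reproduces.

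**Events available.** Section 4.1 expects 12-16% at one year: 0.12 × 218 = 26.2 and 0.16 × 218 = 34.9, so 26-35 events.

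| Cox terms | Events per term |
|---|---|
| IMR + 2 covariates (3) | 8.7-11.6 |
| IMR + 3 covariates (4) | 6.5-8.7 |
| IMR + the 7 predictors named in sections 2.2.2 and 4.2 (8) | 3.3-4.4 |

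The seven are age, sex, infarct area, Killip class, number of PCI, smoking and cholesterol, each counted as one term.

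**Simulation set-up.** N = 218, 14% mean 1-year risk, exponential times censored at one year, likelihood-ratio tests. The ROC cut-off is the Youden point between the 10th and 90th percentiles, with high IMR taken as high risk. Risk shapes, covariate slopes (per SD) and correlations are assumptions, because the documents give none.

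**Optimism of the cut-off, followed as written.** Under a smooth gradient giving 7%/21% either side of the median, the median hazard ratio at the same-data cut-off was 4.89, against 3.21 in the population for the same cut-offs. The ratio is 4.89 / 3.21 = 1.52. A second run gave 5.0 against 3.3.

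**Form of IMR in the Cox model when IMR has no effect** (one covariate, slope 0 / 0.5 / 0.8; 6,000 studies each):

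| Form of IMR | Share significant at 0.05 |
|---|---|
| Continuous, fixed in advance | 5.4% / 5.1% / 5.3% |
| Median split, fixed in advance | 5.3% / 5.6% / 5.2% |
| Best of the 25/50/75% cuts | 12.7% / 13.4% / 13.5% |
| Same-data ROC cut-off | 20.6% / 20.4% / 18.9% |

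The median hazard ratio at that ROC cut-off was about 1.7 when the truth is 1.0. The inflation depends on convention: without the percentile limit it is 22-24%, and with the limit but either direction of risk allowed it is 29-40%, depending on the test and covariates assumed.

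**Covariate screening alone.** A factor was kept only if its median-split log-rank p was below 0.05, with IMR having no independent effect and correlating 0.2 or 0.4 with the factor. Slopes of 0.3, 0.5 and 0.8 passed the screen in about 25%, 57% and 90% of studies. IMR was then significant in 5-8% of screened models, against about 5% with the factor forced in.

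**The case against.** The strongest reply is that most of the harm shown comes from a step the plan does not describe. The Cox sentence follows the risk-factor screening and most naturally serves the secondary objective on predictors of outcome. The better cut-off is a separate secondary endpoint with its own ROC sentence, and nothing passes it into the Cox model. If IMR enters, the median split is the obvious form, since sections 4.1 and 4.2 both use it, and that form keeps the error rate near 5%. Section 4.2 already promises 95% confidence intervals and, in general terms, multiplicity corrections. No adjusted IMR estimate is promised, so part of the remedy is an addition.

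Much of this stands. IMR probably would be included, any one fixed form is adequate, and insisting on a continuous term would be partly preference. A reader might infer that the plan will use a data-derived cut-off as its Cox term, or that p-value screening by itself badly inflates the IMR result. The text does not support the first, and the 5-8% figure does not support the second.

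Two things remain. The screened, open-ended entry rule is what the plan states, and it is a poor rule for 26-35 events. The ROC cut-off is to be found and judged in one data set, so its optimism does not depend on what the Cox model contains.

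**Conclusion.** The point holds as a modest pre-specification weakness in the secondary analyses, and it is cheap to repair. A reader might go further and conclude that the primary result is unsound or that the trial wrongly claims independent prediction. Neither follows: the chi-square is a valid test of association with reproducible power, and the documents make no claim of independence.

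Followed as written, the cut-off would look too favourable, with a hazard ratio overstated by about half under the smooth-gradient assumption. Conditional on the cut-off being carried into the Cox model, the false-positive rate for IMR is about 20% rather than about 5%. The exact figures rest on assumed risk shapes, covariate effects and search convention. The direction does not.

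**What to change.** Keep the chi-square as primary and leave the sample size alone. In the Secondary Objective Analysis of section 4.2:

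1. Pre-specify one supportive Cox model of the 1-year composite in which IMR is always included in one form, stated once: either the primary median split or continuous IMR. Name the IMR measurement used, since sections 2.4 and 3.2.1 describe culprit and non-culprit measurements.
2. Name two or at most three baseline covariates, not chosen by univariable p-values; for example age, and Killip class as a single term with its grouping stated.
3. Report unadjusted and adjusted hazard ratios with 95% confidence intervals whatever the p-value.
4. Label the screened model, and any model using a quantile or ROC cut-off found in these data, as exploratory. Report the cut-off's performance with bootstrap optimism correction.

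There is a natural point by which to settle this: "Data analysis will begin when all patients enrolled in the specified period will have completed 12 months of follow-up". Because section 4.2 also allows ad-interim summary tables on request, the wording should be fixed before any table relating IMR to outcome is produced.

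No new data are needed. Table 1 already collects IMR, demographics and risk classifications, and Appendix A defines Killip class at admission. If the sponsor regards this as a major change, section 6.3 requires an amendment with ethics committee approval.

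The statistical costs are a less favourable cut-off estimate and, if continuous IMR is chosen, lower power should risk be a single step at the median (about 67% against 83% for the split, unadjusted). Adjusted power for continuous IMR could fall to about 62% if IMR correlates 0.4 with a strong prognostic factor (slope 0.8), so the adjusted result should be read from its estimate and interval.
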